9.4.4. Patient-Reported Outcomes and Medical Resource Utilization

Time to sustained worsening of worst pain is defined from the randomization to the time of the first increase (≥ 2 points) in the weekly average of the worst pain score with confirmation in the next consecutive week. Time to sustained worsening of worst pain will be summarized for each arm by the Kaplan-Meier method and will be compared between the 2 arms using the stratified log-rank test.

Time to worsening of physical function is defined as the time from randomization to the first \geq 10-point decrease from baseline with confirmation at the next cycle. Time to worsening of physical function will be summarized for each arm by the Kaplan-Meier method, and the stratified log-rank test will be used to compare between the 2 arms.

For each participant with data from baseline and at least 1 post-baseline visit, the change from baseline at each time point, and maximum change from baseline score will be calculated for each scale of each instrument. The reason and number of missing and incomplete questionnaires and/or assessments by visit will be summarized for each instrument and arm.

Frequency counts of hospitalizations, emergency room visits, radiation, surgery, transfusion, and analgesic use will be summarized descriptively for each arm.

Full censoring rules for these endpoints will be described in the SAP. All the analyses will be conducted for each comparison (Arm A versus Arm B in the ITT and the *ESR1*-mutation detected populations and Arm C versus Arm A in the ITT population) per the prespecified analysis populations. Further analysis details will be described in the SAP.

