9.4.5. Safety Analyses

Safety analyses will be based on the safety population, including the summaries of the following:

- AEs, including severity and possible relationship to study drug
- SAEs, including possible relationship to study drug
- AEs leading to dose adjustments
- discontinuations from study treatment due to AEs or death, and
- treatment-emergent abnormal changes in laboratory values, vital signs, and ECGs.

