2.1. Multiplicity Adjustment

To adjust for multiplicity and control, the overall type I error rate at 0.025 (1-sided), a graphical approach (Bretz et al. 2009; Mauer and Bretz 2013) will be used to test the 3 PFS primary endpoints and the 3 key secondary overall survival (OS) endpoints. Besides, the Lan-DeMets stopping boundaries (O'Brien-Fleming type) will be used to derive the boundaries for the interim and final analyses for PFS and OS in order to control the Type I error rate. Further details are provided in Section 4.3.3.

3. Analysis Populations

For the purposes of analysis, the following analysis populations are defined:

Population	Description	
ITT	All participants randomly assigned to study treatment, regardless of whether they take any doses of study treatment, or if they took the correct treatment. Participants will be analyzed according to the treatment group to which they were assigned. The full ITT population is all participants randomly assigned to study treatment, regardless of concurrent enrollment or not.	
Safety	All participants randomly assigned to study treatment and who take at least 1 dose of study treatment. Participants will be analyzed according to the study treatment they actually received.	
ORR Evaluable	The subset of participants from the ITT population who have measurable disease per RECIST v1.1 at baseline.	
Per-protocol (PP)	All randomized participants (ITT population) who do not have important protocol deviations (IPD) that could potentially affect the efficacy conclusions of the study. See Section 6.2 for details.	
Analysis Population for Arm A vs Arm B in the ITT population	All participants randomized to Arm A and Arm B (N = approximately 640)	
Analysis Population for Arm A vs Arm B in the ESR1 -mutation detected population	The subset of participants with ESR1 mutation detected in the analysis population for Arm A versus Arm B in the ITT population	
Analysis Population for Arm C vs Arm A in the ITT population	Participants concurrently randomized to Arm A and Arm C (N = approximately 440)	

Abbreviations: ITT = intention-to-treat; N = total number of participants; ORR = objective response rate; OS = overall survival; PFS = progression-free survival; RECIST 1.1 = Response Evaluation Criteria in Solid Tumors, version 1.1.

The ITT population is used to analyze endpoints related to the efficacy objectives, and the safety population is used to analyze the endpoints and assessments related to safety.

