4.4.2. Supportive Secondary Endpoints

All supportive secondary endpoint analyses will be conducted for each comparison (Arm A versus Arm B, and Arm C versus Arm A) per the prespecified analysis population for each comparison.

Objective response rate (ORR) is defined as the proportion of participants who achieve a confirmed best overall response of CR or PR. The ORR with 95% CI will be summarized for each treatment arm and compared between treatment arms using the Cochran-Mantel-Haenszel test adjusting for the randomization strata. The analysis of ORR will be conducted in the ORR evaluable population. The Mantel-Haenszel estimate of the common risk difference of ORR with 95% CI between 2 arms will also be estimated.

Clinical benefit rate (CBR) is defined as the number of participants who achieve a best overall response of CR, PR, or SD \geq 24 weeks divided by the total number of participants randomized to the corresponding treatment arm. The CBR with 95% CI will be summarized for each treatment arm and compared between treatment arms using the Cochran-Mantel-Haenszel test adjusting for the randomization strata. The Mantel-Haenszel estimate of the common risk difference of CBR with 95% CI between 2 arms will also be estimated.

Duration of response (DoR) is defined as the time from the date measurement criteria for CR or PR (whichever is first recorded) are first met until the first date that disease is recurrent or objective progression is observed, per RECIST 1.1 criteria, or the date of death from any cause

in the absence of objectively determined disease progression or recurrence. The DoR will be censored according to the same scheme as the main scheme for PFS. Median DoR with 95% CI and curves for each treatment arm will be estimated using the Kaplan-Meier method. The analysis of DoR will be based on the participants who achieve an objective response (CR or PR).

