The severity of laboratory results will be classified according to NCI-CTCAE. The laboratory toxicity by worst NCI-CTCAE grade and shifts in toxicity grading from baseline to the worst post-baseline grade will be summarized. Abnormal laboratory parameters will be listed.

Shift to low/high tables will include the number and percentage of patients within each baseline category (baseline value is low, normal, high, or missing) versus each postbaseline category (worst value is low, normal, high, or missing) by treatment arm.

The analyses of adverse events, deaths, and laboratory abnormalities will be conducted in the safety population.

Time to sustained worsening of worst pain (as measured by the Worst Pain NRS) is defined as the time from randomization to the first increase (≥ 2 points) in the weekly average of the worst pain score with confirmation in the next consecutive week. See Section 4.6 for further details.

Pharmacokinetic/Pharmacodynamic Analyses

PK parameters for imlunestrant in plasma (for example, clearance, volume of distribution) and inter-individual PK variability will be computed using nonlinear mixed-effect modeling implemented in NONMEM. Covariate effects, such as age, weight, sex, and creatinine clearance, on the PK parameters of imlunestrant in plasma will also be investigated.

Biomarker data collected in this study may be used in a population PK/pharmacodynamic model.

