4.6. Patient-Reported Outcomes Analyses

The patient reported outcomes (PROs) will be used to compare changes in cancer-related symptoms, physical function, adverse effect of diarrhea, and other health-related quality of life (HRQoL) outcomes between treatment arms and generate health utility data. The analyses for PROs will be conducted in the ITT population. The following PRO instruments are utilized:

- Worst pain NRS
- EORTC-QLQ-30
- EORTC IL19: Physical Function
- EQ-5D-5L
- PGIS (Patient's Global Impression of Severity)-Cancer Symptoms
- mBPI-SF
- PRO-CTCAE Items for Diarrhea and Injection Site Pain and Swelling

Time to sustained worsening of worst pain (based on the Worst Pain NRS) is defined as the time from randomization to the first increase (≥ 2 points) in the weekly average of the worst pain score with confirmation in the next consecutive week. Participants not known to have sustained worsening will be censored at the last documented assessment. Time to sustained worsening of worst pain will be summarized for each arm by the Kaplan-Meier method and will be compared between the arms using the stratified log-rank test. Additional cutoff values of increase (e.g., ≥ 3 points, ≥ 4 points) may be explored as sensitivity analyses if deemed appropriate. Sensitivity analysis will be done by including death as part of the event definition. Additional sensitivity analyses for time to worsening without confirmation in the next consecutive week may be performed if deemed appropriate. A standard analgesic categorization algorithm such as WHO analgesic ladder will be used to analyze the data, along with the worst pain, as an additional analysis. This will be detailed in the PRO SAP.

Time to worsening of physical function (based on either EORTC-QLQ-30 or EORTC IL19) is defined as the time from randomization to the first \geq 10-point decrease from baseline with confirmation at the next cycle. Participants not known to have worsening will be censored at the last documented assessment. Sensitivity analysis will be done by including death as part of the

event definition. Time to worsening of physical function will be summarized for each arm by the Kaplan-Meier method, and the stratified log-rank test will be used to compare between the 2 arms.

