For EORTC-QLQ-30, EORTC IL 19, EQ-5D-5L, mBPI-sf, PGIS, a summary of change from baseline will be provided. For each participant with data from baseline and at least 1 post-baseline visit, change from baseline at each time point, and the maximum change from baseline score will be calculated for each scale of each instrument if appropriate.

PRO-CTCAE items for diarrhea and injection site pain and swelling will be summarized by visit and overall for each treatment arm.

Compliance will be assessed for each instrument. The compliance rate will be calculated at baseline, per week (if appropriate) and per cycle. The number of participants with expected assessments at each post-baseline visit is the number of participants who have received the study drugs in a previous visit. For the Worst Pain NRS, participants will be considered compliant if they have completed \geq 50% of the daily assessments during each period (e.g., week, cycle). A 7-day average score regardless of dosing will be calculated for each consecutive week starting from cycle 1 day 2, if the participant is compliant for the period (completed 4 days out of the 7-day period). A 7-day average score based on any available data may also be calculated as sensitivity analysis even if the compliance rate is lower than 50%. For other instruments, the number of missing and incomplete questionnaires and/or assessments by visit will be summarized for each instrument and treatment arm.

The cycle 1 day 1 (pre-dose) visit will be considered as baseline for all PRO analyses. The analysis for change from baseline will be based on the participants who have baseline and at least 1 post-baseline data.

Further details about PRO analyses will be described in a separate PRO SAP.

4.7. (Other) Safety Analyses

The other safety analyses will be conducted in the safety population.

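### No concurrent safety set is defined for Arm C versus Arm A, so crude death and adverse-event tables would set Arm C against an Arm A holding about 100 patients not randomized against it

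*SAP*

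**What the plan says.** SAP Section 3 defines the population for Arm C versus Arm A as the roughly 440 participants concurrently randomized to those arms, and SAP 4.3.2 and 4.4.1.2 use it for PFS and OS. The set of all randomized participants carries a separate label (full ITT). For C versus A it appears only in PFS and OS sensitivity analyses.

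Safety is handled differently. SAP Section 3 defines the safety population as "All participants randomly assigned to study treatment and who take at least 1 dose of study treatment", with no concurrency condition. SAP 4.4.2 then says "The analyses of adverse events, deaths, and laboratory abnormalities will be conducted in the safety population". SAP 4.7 adds "The other safety analyses will be conducted in the safety population", and Protocol 9.4.5 says "Safety analyses will be based on the safety population, including the summaries of the following". None of these places defines a safety set for C versus A. The planned death summaries in SAP 4.4.2 include all deaths as well as deaths within 30 days of stopping treatment.

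SAP 4.4.2 opens with a rule that supportive secondary analyses follow the prespecified population for each comparison. The populations it points to are ITT-based, and the adverse-event, death and laboratory text in the same section then names the safety population instead.

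**The concern.** The SAP treats concurrency as necessary for a fair C-versus-A efficacy comparison. Followed as written, the safety tables would place about 220 Arm C patients beside about 320 Arm A patients, some of whom were randomized only between A and B, either before Arm C opened or at sites that had not yet implemented it. Those patients entered earlier and have been observed longer. A crude percentage that accumulates with calendar time, such as all deaths, is then higher in Arm A even when the two treatments carry identical risk. That makes the combination look better against monotherapy than it is, in a table a benefit-risk reader will look at.

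Follow-up may not be the only difference. The protocol's amendment history shows that the amendment which opened Arm C also changed some eligibility limits and added safety visits. Some two-arm patients may have entered under other rules. The documents do not allow this to be quantified.

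**Working it through.** **Inputs (SAP Section 5).** Total monthly accrual is 5, 10, 15, 20, 25, 35, 35, 35, 35, 35, 40, 40, 40, 40, then 45. Arm C enters after 6 months. Three-arm accrual is then 15, 15, 18, 18, 36, 36, 36, 36, then 45. Two-arm accrual is the difference. All arms close when A plus B reaches 640.

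**Step 1: reproduce the planned enrolment.**
- First 14 months: total 410, three-arm 210, so two-arm 410 − 210 = 200.
- A plus B at month 14: 200 + 210 × 2/3 = 340. The remaining 300 accrue at 30 per month, so enrolment closes at month 24.
- Three-arm total: 210 + 450 = 660. Arm C = 660/3 = 220. Arm A = 200/2 + 220 = 320, and Arm B is the same. Total 860, as the SAP states.

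**Step 2: non-concurrent Arm A.** 200/2 = 100 of 320 (31%). Of these, 110/2 = 55 enter before Arm C opens and 45 enter later at sites without it.

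**Step 3: entry times (month midpoints).** Mean randomization month is 6.0 for two-arm and 16.4 for three-arm patients, a difference of 10.3 months. Averaged over Arm A, the follow-up excess is (100/320) × 10.3 = 3.2 months.

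**Step 4: crude deaths with no true difference.** SAP Table 4.3 plans for 65 deaths at the final C-versus-A PFS analysis. Over 440 patients that is 65/440 = 14.8%. Assume one constant hazard λ for all patients and no dropout. The proportion dead is the average of 1 − exp(−λ × follow-up) over entry times, with λ solved so that three-arm patients show 14.8%. The cut-off month is an assumption. With PFS medians of 5.8 and 5.8/0.7 = 8.3 months, 248 events fall at about month 26, and months 28 and 30 allow for slippage.

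| Cut (month) | λ per month | Arm C and concurrent A | Two-arm A | Full Arm A | Gap (points) |
|---|---|---|---|---|---|
| 26 | 0.0169 | 14.8% | 28.6% | (100 × 28.6 + 220 × 14.8)/320 = 19.1% | 4.3 |
| 28 | 0.0139 | 14.8% | 26.3% | 18.4% | 3.6 |
| 30 | 0.0118 | 14.8% | 24.7% | 17.9% | 3.1 |

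With the same three hazards, the gap is 2.9 to 3.6 points at month 36 and 2.2 to 2.4 points at month 60. As a cross-check, the median OS of 2 to 3 years in Protocol Section 2 gives a gap of 4.8 to 6.3 points at about month 26.

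**Step 5: adverse events.** Assume exponential time on treatment with median 5.8 months and an onset hazard of 0.02, 0.05 or 0.10 per month while on treatment. At about month 26, incidence is 9.6%, 21.5% and 36.4% in concurrent Arm A against 10.8%, 23.6% and 39.0% in full Arm A, differences of 1.2 to 2.6 points. At month 36 the differences are below 0.5 point.

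**Step 6: direction for adverse events.** At the planned hazard ratio of 0.7, taking treatment time as PFS, mean exposure at month 26 is 6.2 months in Arm C, 6.0 in full Arm A and 5.3 in concurrent Arm A. Full Arm A is closer to Arm C in exposure, so no net bias in favour of the combination is shown.

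**The case against.** A reader might infer that ORR and patient-reported outcomes suffer in the same way, since SAP 4.4.2 says "The analysis of ORR will be conducted in the ORR evaluable population", SAP Section 3 defines that set as "The subset of participants from the ITT population who have measurable disease per RECIST v1.1 at baseline", and SAP 4.6 says "The analyses for PROs will be conducted in the ITT population". The documents do not support that reading. The opening rule of SAP 4.4.2 and Protocol 9.4.3.3 assign these analyses to each comparison's own population, and the ORR-evaluable set is a measurable-disease filter within it. For patient-reported outcomes Protocol 9.4.4 says "All the analyses will be conducted for each comparison" and lists the populations, including the ESR1-mutation detected one. SAP 4.6 is loosely worded, does not invoke full ITT, and defers details to a separate PRO SAP, so it cannot be said to drop an analysis. The PRO time-to-worsening endpoints are also censored, so longer follow-up alone would not bias them.

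On safety, the case against is that the tables are descriptive by arm and no C-versus-A safety test is specified. Inference on mortality comes from OS, which is restricted to concurrent patients and analysed by Kaplan-Meier and log-rank methods. The SAP also plans time to onset for selected events, deaths within 30 days of stopping treatment and, if deemed appropriate, cumulative incidence at 3 months, 6 months and 1 year.

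This stands as a limit on the consequences: no hypothesis test is affected. It does not remove the gap, because the crude all-deaths table is still planned on the unrestricted set and the fixed-time adverse-event summaries are optional.

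**Conclusion.** The concern holds for safety. As written, C-versus-A safety tables would use all dosed Arm A patients, about 31% of whom were not randomized against Arm C. The crude all-deaths percentage in Arm A would be raised by about 3 to 4 points at an assumed cut of months 26 to 30, shrinking to about 2 to 3 points later, with no true difference between arms. This rests on the SAP's accrual assumptions, its 65-death planning count, a common constant hazard, no dropout, and everyone being dosed.

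Two stronger inferences are not supported. The 10-month difference belongs to the 100 non-concurrent patients; over Arm A as a whole it is 3.2 months. For adverse events the effect of full Arm A is only about 1 to 3 points at month 26, on assumed onset rates, and its net direction is not established. The change is worth making before the final tables, mainly for deaths.

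**What to change.** In SAP Section 3, add a safety set for Arm C versus Arm A: dosed participants concurrently randomized to Arms A and C, about 220 against 220. Name it in SAP 4.4.2 and 4.7 for every side-by-side C-versus-A safety table, above all the crude all-deaths table. Keep full Arm A for A versus B and for per-arm summaries.

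As a wording alignment only, state in SAP 4.6 that PRO analyses follow the prespecified population for each comparison, to match Protocol 9.4.4.

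The cost is a few lines of SAP text and one further set of tables. Arm A falls from about 320 to about 220 in the C-versus-A safety tables, so rare events are estimated less precisely there. Alpha, power and trial conduct do not change.

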4.5. Exploratory Endpoints Analysis

All the exploratory analyses will be conducted for each comparison (Arm A versus Arm B and Arm C versus Arm A) per the prespecified analysis population for each comparison if the number of events is sufficient, unless otherwise stated.

Time to progressive bone metastases is defined as the time from randomization to the date of earliest development of new bone metastases or unequivocal progression of current bone lesions. Participants not known to have progressive bone metastases will be censored at the date of last documented tumor assessment. Time to progressive bone metastases will be summarized for each treatment arm using the Kaplan-Meier method and will be compared between 2 arms using the log-rank test.

Time to first skeletal-related event (SRE) is defined as the time from randomization to the first SRE defined as either pathological fracture, spinal cord compression, radiation to the bone, or surgery to the bone. Participants not known to have an SRE will be censored at the date of last documented assessment. Time to first SRE will be summarized for each treatment arm using the Kaplan-Meier method and will be compared between 2 arms using the log-rank test.

Time to chemotherapy (TTC) is defined as the time from randomization to the initiation of first post-discontinuation chemotherapy. Participants who die prior to the initiation of chemotherapy will be censored at the date of death. TTC will be summarized for each treatment arm using the Kaplan-Meier method and will be compared between 2 arms using the log-rank test.

Chemotherapy-free survival (CFS) is defined as the time from randomization to the initiation of first post-discontinuation chemotherapy or death, whichever is earlier. Participants not known to have initiated chemotherapy will be censored at the last documented assessment. CFS will be summarized for each treatment arm using the Kaplan-Meier method and will be compared between 2 arms using the log-rank test.

Progression-free survival 2 is defined as the time from randomization to objective disease progression on the next line of treatment or death, whichever is earlier. Participants alive and not known to have a second objective progressive disease will be censored on the latest date known to be alive and without a second objective disease progression. PFS2 will be summarized for each treatment arm using the Kaplan-Meier method and will be compared between 2 arms using the log-rank test. Sensitivity analysis for PFS2 will be performed if deemed appropriate. For example, instead of objective disease progression, we may conduct analysis including clinical disease progression.

Time to worsening of ECOG PS of ≥ 2 is defined as the time from randomization to the date when ECOG PS score of ≥ 2 was observed for the first time. Participants not known to have such worsening will be censored at the last time when no worsening of ≥ 2 is observed. Time to worsening of ECOG PS of ≥ 2 will be summarized for each treatment arm using the Kaplan-Meier method and will be compared between 2 arms using the log-rank test.

PFS and OS will be compared between Arm C and Arm B using the stratified log-rank test. The treatment effect will be estimated by hazard ratio with its corresponding 95% CIs using the stratified Cox proportional hazard model. The analysis population for Arm C versus Arm B is all concurrently randomized participants between 2 arms. Subgroup analyses (e.g. based on stratification factors) will be conducted if deemed appropriate. Other efficacy endpoints may also be compared between Arm C and Arm B if deemed appropriate.

